5.2.1 Data Collection and Follow-up for Withdrawn Subjects

Subjects who withdraw consent to participate in the study will be seen for one final study visit. During this visit they will be asked for permission to assess their survival status via medical records.

6 Statistical Plan

The study design will allow multiple comparisons; specifically baseline to intervention group and cross-unit comparisons. The specific aim of the study is to pilot test **RESTORE resilience**, an individualized chronotherapeutic bundle, in pediatric patients supported on mechanical ventilation for acute respiratory failure in the PICU. The study design is a two-phase prospective cohort study. Subjects will be consecutively enrolled into the Baseline Phase and then into the Intervention Phase in two separate PICUs. Each unit will enroll 10 baseline subjects followed by 20 intervention subjects (total: 20 baseline subjects and 40 intervention subjects). Outcome variables are designed to be as objective as possible since it is not possible to blind the assessor to treatment phase.

6.1 Sample Size and Power Determination

This study is not powered for effect. As a pilot study we are only interested in evaluating the feasibility of implementing all elements of the RESTORE-resilience intervention (see below).

6.2 Statistical Methods

For purposes of this pilot study, we assume that subjects managed per R2 will exhibit maintain circadian rhythmicity and demonstrate an improved sleep-wake pattern, as evidenced by increased circadian activity ratio (daytime activity/total 24-hr activity) post-extubation, compared to those managed per usual care. Preliminary data from current studies in the PICU suggest that 50% of activity occurs during the nighttime hours in the PICU. We anticipate that the R2 intervention will result in a decrease in nighttime activity to 30% of total activity. **This pilot study is exploratory to determine preliminary estimates in order to develop power calculations for a future trial.**

6.3 Control of Bias and Confounding

To avoid bias all eligible subjects will be consecutively approached for consent and we will use objective biological endpoints.

6.3.1 Baseline Data

Baseline and demographic characteristics will be summarized by standard descriptive statistics (including mean and standard deviation for continuous variables such as age and standard percentages for categorical variables such as gender).

6.3.2 Analysis of Primary Outcome of Interest

Analysis of the primary outcome: Average circadian activity ratio, defined as daytime activity/total 24-hr activity, after extubation as demonstrated by actigraphy. Daytime will be defined as 7 am -7 pm. Validated in infants and children, actigraphs capture activity counts in 1-minute epochs which can be compared between daytime and nighttime hours as a marker of circadian rhythm. Because activity levels vary between patients (i.e., a child with cerebral palsy and/or muscle weakness will not produce the same activity amplitude as a healthy child), the circadian activity ratio provides a method of normalizing the data to account for each patient's baseline amplitude. Increases in the daily circadian activity ratio would suggest improvement in day-night rest-activity patterns and sleep consolidation over time.

7 Safety and Adverse Events

All enrolled subjects are critically ill and no additional study-related risk is anticipated. This section provides the safety management plans for the study if one were to occur. The MPIs will be responsible for ensuring the safety of participants on a daily basis. The MPI and the study coordinators will meet bi-weekly to review current status of the protocol. The bi-weekly meetings will assess the safety of the patients enrolled on the study.

7.1 Definitions

7.1.1 Adverse Event

Patients will be monitored for the occurrence of events defined as any undesirable experience or unanticipated benefit. Patients will be monitored daily to determine whether an event has occurred. All adverse events will be recorded on an adverse event case report form. Serious adverse events (death, life threatening, new serious or permanent disability) will be reported within 24 hours to the MPI team within 72 hours to the Institutional Review Board (IRB). Recommended protocol modifications will be implemented immediately. A description of all undesirable experiences or unanticipated benefits will be recorded on the case report form. In addition, the required interventions, patient's condition after the event, an estimate of the extent of injury, and prevention strategies will be reported. The relationship of the study protocol to the event will be classified by a consensus of the bedside team as follows:

- Not related: The event is clearly related to factors such as the subject's clinical state, not with therapeutic interventions associated with the study protocol.
- Remote: The event was most likely related to factors such as the subject's clinical state, not with therapeutic interventions associated with the study protocol.
- Possible: The event follows a reasonable temporal sequence from the implementation of the protocol and/or is consistent with known events related to the protocol but is possibly related to factors such as the subject's clinical state.
- Probable: The event follows a reasonable temporal sequence from the implementation of the protocol and/or is consistent with known events related to the protocol and cannot be reasonably explained by factors such as the subject's clinical state.
- Highly Probable: The event follows a reasonable temporal sequence from the implementation of the protocol and/or is consistent with known events related to the implementation of the protocol and cannot be reasonably explained by factors such as the subject's clinical state. In addition, the event occurs immediately following the implementation of the protocol, or improves when discontinuing the protocol, or reappears on the repeat implementation of the protocol.

7.1.2 Serious Adverse Event

The severity of an adverse event in both phases is defined as a qualitative assessment of the degree of intensity of an adverse event as determined by a consensus of the bedside team as follows:

- Mild: Does not impact (in anyway) the patient's course of illness.
- Moderate: Impacts the subject's course of illness but is not life-threatening or incapacitating.
- Severe: Fatal, life threatening, permanently disabling; severely incapacitating; requires/prolongs inpatient hospitalization.

The principal investigators will immediately follow-up on all serious events on a case-by-case basis. All adverse events will be summarized and reviewed on a monthly basis.

7.2 Recording of Adverse Events

At each contact with the subject, the investigator will seek information on adverse events by specific questioning and, as appropriate, by examination. Information on all adverse events will be recorded immediately in the source document, and also in the appropriate adverse event module of the case report form (CRF). All clearly related signs, symptoms, and abnormal diagnostic procedures results will be recorded in the CRF.

All adverse events occurring during the study period will be recorded. All study related SAE's will be reported to the IRB in writing by the MPI within 24 hours of the event. The following guidelines will be followed: 1) A letter will summarize any adverse events or events that occurred, the patient's name will not be included. The event outcome will be described. 2) An original and 3 sets of documents including the letter, any communication from the study team, and all supporting documents will be provided. The clinical course of each event will be followed until resolution, stabilization, or until it has been determined that the study intervention or participation is not the cause. Serious adverse events that are still ongoing at the end of the study period will be followed up to determine the final outcome. Any serious adverse event that occurs after the study period and is considered to be possibly related to the study intervention or study participation will be recorded and reported.

7.3 Relationship of AE to Study

Following discussion with the attending physician and clinical care team, review of the medical records and any applicable CRFs, the PI will determine the relationship and classification of all AEs.

7.4 Reporting of Adverse Events and Unanticipated Problems

The Investigator will promptly notify the Penn IRB of all on-site unanticipated, Adverse Events that are related to the research activity. Other unanticipated problems related to the research involving risk to subjects or others will also be reported promptly. Written reports will be filed within HS-ERA within 10 working days.

All adverse events that are previously undescribed, or serious and study-related are subject to expedited reporting. The NIH will be notified (by telephone, fax, or writing) as soon as possible but no later than 7 calendar days after first knowledge by investigator that a case qualifies, followed by as complete a report as possible within 8 additional calendar days. The NIH report will include:

- Patient details: initials, subject number, gender, age and/or DOB, weight, and height.
- Intervention that resulted in AE or SAE
- Other treatments (same as above) for all other concomitant medicinal products.
- Details of the SAE: description of the event (signs and symptoms/diagnosis); why this is considered serious (criteria); onset and duration of the event; dechallenge/ rechallenge information; setting.
- Outcome: information on recovery and any sequelae; specific treatments/tests and results; cause of death; autopsy or post mortem reports.
- Reporter - name, profession, address, and phone number.
- Determinants of causality - temporal (time) association, known AEs, subject's current state of health, response to dosage change, concomitant medications, other therapies the subject is undergoing.

7.4.1 Follow-up Report

If an AE has not resolved at the time of the initial report and new information arises that changes the investigator's assessment of the event, a follow-up report including all relevant new or reassessed information (e.g., concomitant medication, medical history) will be submitted to the IRB.

7.4.2 Data and Safety Monitoring Plan

A DSMB will not be required for this study. The PI will monitor this study. Local investigators will contact [name] immediately, should any unanticipated problems occur. Patients will be monitored for the occurrence of events defined as any undesirable experience or unanticipated benefit. Patients will be monitored daily to determine whether an event has occurred.

8 Study Administration, Data Handling and Record Keeping

8.1 Confidentiality

Information about study subjects will be kept confidential and managed according to the requirements of the Health Insurance Portability and Accountability Act of 1996 (HIPAA). The parental permission form for this study informs the parent/subject of the following:

- What protected health information (PHI) will be collected in this study
- Who will have access to that information and why
- Who will use or disclose that information
- The rights of a research subject to revoke their authorization for use of their PH.

After providing informed consent/parental permission/assent, the subject will be assigned a unique case number. This number will be used to label all private research information, including clinical assessments and saliva swabs. Original signed informed consent forms will be kept in a locked cabinet in a private office. All data and photographs will be entered directly into a password-protected database that will be maintained on a password-protected network drive. Access to the server is through a password-protected account that allows access to data collected only to the investigator and their designees. Consent logs and other research records will be kept for 7 years after the primary paper is published for audit purposes. At that time, they may be destroyed under the direction of the Principal Investigator. Results will only be reported in aggregate form.

In the event that a subject revokes authorization to collect or use PHI, the investigator, by regulation, retains the ability to use all information collected prior to the revocation of subject authorization. For subjects that have revoked authorization to collect or use PHI, attempts will be made to obtain permission to collect at least vital status (i.e. that the subject is alive) at the end of their scheduled study period.

8.2 Data Collection and Management

The Data Coordinating Center (DCC) will work with the MPI team to develop a web-based Data Management System (DMS) using the REDCap electronic data capture system. According to programmed workflow logic, the DMS will generate electronic Case Report Forms as needed for each patient (e.g., daily forms, study discharge form). The DMS allows for the data to be viewed in real time by the DCC staff and certified data entry personnel at the clinical sites. Many automated logic and range checks and cross-form validations will be programmed to ensure data quality, and audit trails will be maintained.

The DCC will work with each clinical center to ensure that database training and certification is obtained by all new staff and that data are entered, data queries are resolved, and data-related questions are answered promptly.

The DCC will transfer electronic data files as needed in a secure and confidential manner. The DCC will also create reports as needed by the NIH, for study quality review (e.g., monthly protocol adherence reports), and for review as needed by our Data and Safety Monitoring Plan.

Confidentiality will be maintained throughout the study in the following ways:

- 1) All data will be de-identified then stored in the secure REDCap database or in the Excel database, as appropriate.
- 2) Specimens will be de-identified and stored in lockable research freezers, and each participant will be assigned a unique identification number.
- 3) A master list (linking PHI to study ID) will be housed separately from all data forms (both paper and electronically). The master list will be maintained by the PI and stored in a password protected file within Excel on computers on accessible by the study team and password protected.

CONFIDENTIAL

8.3 *Records Retention*

Study records will be retained per applicable NIH and Penn IRB requirements. Records will be stored in locked cabinets, in locked offices only accessible to the study team.

9 *Study Monitoring, Auditing, and Inspecting*

9.1 *Study Monitoring Plan*

The study MPIs will be responsible for ensuring the ongoing quality and integrity of the research study.

9.2 *Auditing and Inspecting*

The investigator will permit study-related monitoring, audits, and inspections by the EC/IRB, the sponsor, government regulatory bodies, and University compliance and quality assurance groups of all study related documents (e.g. source documents, regulatory documents, data collection instruments, study data etc.). The investigator will ensure the capability for inspections of applicable study-related facilities (e.g. pharmacy, diagnostic laboratory, etc.).

10 *Ethical Considerations*

10.1 *Risks*

Privacy and Confidentiality: Strict measures will be taken to ensure participant privacy and confidentiality. All data will be de-identified then stored in the secure REDCap database or in the Excel database, as appropriate. Specimens will be de-identified and stored in lockable research freezers, and each participant will be assigned a unique identification number. The master list linking identification numbers to identifying information will be stored separately from the study database. All personally identifiable information will be kept strictly confidential and stored in an encrypted document, on a dedicated research server only accessible by the research team.

Risk associated with EEG and ankle/wrist monitoring includes irritation at the site and will be minimized by scheduled assessments of the sites, and removal of the device if irritation or redness occurs.

The major components of RESTORE are a standard of care in each PICU. The current study is testing the feasibility of implementing the entire 7-item bundle of activities/clinical care within a PICU, it is not testing each item within the bundle. Risk associated with over and /or under sedation will be minimized by hourly assessment of goal SBS attainment with the subject is intubated.

Risks associated with bolus feed included gastro-esophageal reflux and aspiration. However, children who are at risk for reflux and aspiration will be excluded from the study. Children who have clinical signs of aspiration will be removed from study. Reflux precautions including head of bed at 300 will be implemented when appropriate.

Risks from progressive mobility include inadvertent tube/catheter dislodgement. However, these risks are minimized since the care models at both Johns Hopkins and CHOP have incorporated progressive mobility as part of the standard of care, and are well trained with this intervention. Children at high risk for tube and or catheter dislodgment will not participate in this activity.

10.2 *Benefits*

10.3 *Risk Benefit Assessment*

No direct benefit from study participation is expected. Participation may result in the improvement in the environment, daily routine and sleep patterns of children during a stay in the PICU. The findings from this study will increase clinical knowledge regarding the care of critically ill children and how best to preserve and/or restore a child's circadian rhythm. The possible benefits of this study outweigh the risks to participation. We expect these results will contribute to education of pediatric health providers, care of all

CONFIDENTIAL

pediatric patients with acute respiratory failure, and future studies evaluating the effects of environment and care.

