- 9) Activity Log – completed by parent or nurse daily to record patient activities (such as sleep, feeding, etc)

Intervention Phase:

- 1) The local investigator(s) or designee will round separately on each enrolled subject daily and complete the R2 bundle adherence form
- 2) Child's Daily Routine and Sleep Survey – completed at enrollment by a parent
- 3) The provision of cycled day-night lighted and modulation of sound to match the child's routine (provided by the parent)
- 4) Minimum but effective sedation administered per RESTORE process – per medical records

CONFIDENTIAL

- 5) Night fasting with bolus enteral daytime feedings per child's routine feeding schedule (unless contraindicated) – per medical records and activity log
- 6) Documentation of one of three physical activities within the PICU Up! program implemented
- 7) The number of nurses assigned to care for the subject – per activity log
- 8) Parent diary entries – paper or electronic

Within 48 hours of patient PICU discharge; specifically, after transfer to an inpatient unit:

- Parents will be contacted to complete the Family-Centered Care Scale (FCCS)
 - Completed in person if still hospitalized or over the phone or electronically (using a REDCap database)
 - A 7-item measure of parents' experiences with nursing care and perceptions of being well-cared for during a PICU stay

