5.2 Subject Withdrawal

Subjects may withdraw from the study at any time without impact to their care. They may also be discontinued from the study at the discretion of the Investigator for lack of adherence to intervention or

CONFIDENTIAL

This material is the property of the University of Pennsylvania.

study procedures or visit schedules, AEs, or due to a change in medical history (e.g. develop an exclusionary medical condition or medication). The Investigator may also withdraw subjects who violate the study plan, to protect the subject for reasons related to safety or for administrative reasons. It will be documented whether or not each subject completes the study. Subjects who withdraw early will have one final visit to collect final evaluations and assess adverse events.

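### Section 10.1 takes a child with signs of aspiration out of the whole study, and nothing in the plan continues actigraphy or record-based outcomes afterwards

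*Combined protocol and SAP*

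**What the plan says.** Section 10.1 lists reflux and aspiration as risks of bolus feeding. It gives two protections: "children who are at risk for reflux and aspiration will be excluded from the study", and, once an event occurs, "Children who have clinical signs of aspiration will be removed from study". The second is mandatory and refers to the study, not to the feeding element. Whether it applies in the Baseline Phase is not stated.

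Elsewhere the plan deals with problems locally. Section 3.3, Intervention Phase item 5, gives feeds on the child's "routine feeding schedule (unless contraindicated"), so a child can be in the Intervention Phase without this element. For skin problems under the monitors, section 10.1 provides for "removal of the device if irritation or redness occurs". Children at high risk of tube dislodgement skip the mobility activity only.

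On data after early withdrawal, section 5.2 says: "Subjects who withdraw early will have one final visit to collect final evaluations and assess adverse events". It does not define the final evaluations. Section 5.2.1 adds permission to check survival status, for those who withdraw consent. Section 7.2 follows the adverse event to its outcome. Section 8.1 deals with revoked authorization. Section 6 has no analysis-set or missing-outcome rule for removed children.

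**The concern.** The primary outcome (6.3.2) is an average of actigraphy after extubation. Aspiration signs can appear while the child is still intubated. If the child leaves the study then, there is no primary value, and one final visit cannot supply one. Ventilation time, length of stay and sedative exposure come from the medical record (3.3) and could still be abstracted, but the plan does not provide for it.

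The loss would not be random with respect to phase. Bolus feeding is a bundle element in the Intervention Phase, so removals for a feeding-related event would probably fall mostly there. What is left is a comparison of Baseline children with Intervention children who did not show aspiration signs.

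Section 6.1 says the interest is in the feasibility of implementing all elements, and section 2.2 lists feasibility and adherence as outcomes. A child who cannot continue the feeding element is a feasibility result. The plan does not say that such a child stays in the denominator. Sections 2 and 6.2 say the results will inform the design of a later powered trial, so a favourable tilt would carry forward.

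**Working it through.** **Inputs from the plan.** Section 6: two sites, each with 10 Baseline and 20 Intervention children. Check: 2 × (10 + 20) = 60, that is 20 and 40, as stated. Section 6.2: night activity is 50% under usual care and is anticipated to be 30% under R2. The ratio is daytime over total activity, so these become 1 − 0.50 = 0.50 and 1 − 0.30 = 0.70, an anticipated gain of 0.20.

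**Assumptions not in the plan.** It gives no aspiration rate, standard deviation or dropout rate. Take k = 1, 2, 4 or 6 of 40 Intervention children removed; children who stay average 0.70; removed children would have averaged r.

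**Shift in the Intervention mean.**
- (a) All removed before extubation, not replaced: shift = (k/40) × (0.70 − r), for r = 0.50 and r = 0.60.
- (b) Only half removed before extubation, r = 0.50, not replaced: shift = [0.70(40 − k) + 0.50(k/2)]/(40 − k/2) − [0.70(40 − k) + 0.50k]/40.
- (c) All removed before extubation, r = 0.50, each replaced by a child averaging 0.70: the observed mean is 0.70, and the mean over everyone enrolled is (0.70 × 40 + 0.50k)/(40 + k), so shift = 0.20k/(40 + k).

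| k | k/40 | (a) r = 0.50 | (a) r = 0.60 | (b) | (c) |
|---|---|---|---|---|---|
| 1 | 2.5% | 0.005 | 0.0025 | 0.0025 | 0.0049 |
| 2 | 5% | 0.010 | 0.005 | 0.0049 | 0.0095 |
| 4 | 10% | 0.020 | 0.010 | 0.0095 | 0.0182 |
| 6 | 15% | 0.030 | 0.015 | 0.0138 | 0.0261 |

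Column (c) shows that replacement leaves the selection nearly as it was.

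**Precision.** With equal standard deviations and no replacement, the standard error of the phase difference changes by the factor √(1/20 + 1/(40 − k)) / √(1/20 + 1/40) = 1.0043, 1.0087, 1.0184 or 1.0290, a rise of 0.4% to 2.9%. With replacement the count stays at 40 and the factor is 1.

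**Feasibility of the feeding element.** If removed children are counted as unable to continue and all others continue, the result is (40 − k)/40 = 97.5%, 95%, 90% or 85% (for 36/40, exact 95% interval 76% to 97%). If removed children are dropped from the denominator it is (40 − k)/(40 − k) = 100% whatever k is.

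**The case against.** **The rule is a conservative safeguard.** A reader might infer that stopping bolus feeds would be enough after signs of aspiration, and that removal is therefore simply wrong. The documents do not support that. The exception in 3.3 shows that feeding can be omitted; it does not show that mobility or other elements should continue after an aspiration event in a ventilated child. The device rule is a weak parallel, since skin redness is far less serious. Section 10.4 also discontinues participants who become intolerant of the study. This stands, and the clinical response may be as broad as the team wishes. It does not justify ending data collection: wearing an actigraph and having a chart abstracted add no aspiration risk.

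**The bundle is tested whole.** Section 10.1 says of the study that "it is not testing each item within the bundle". That is a possible rationale, but the feeding exception already admits children who do not receive every element, and testing the whole bundle's feasibility is a reason to count its failures.

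**Precision is lost.** A reader might infer this, but it is not settled. Section 4.2 asks each site for 30 children with full usable data, which suggests replacement; section 4.5 ends recruitment at 60 enrolled, which suggests none.

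**Feasibility failures would go unseen.** That too goes beyond the documents. Under 3.3 the investigator or designee "will round separately on each enrolled subject daily and complete the R2 bundle adherence form", section 5.2 documents completion, and section 7.1.1 puts the event on a case report form. The removal would be visible. What is unstated is the denominator, and the plan defines none for any child, so that gap is wider than this sentence.

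**Section 5.2 has the same defect.** Not quite. Its wording is permissive: "They may also be discontinued from the study at the discretion of the Investigator for lack of adherence to intervention". It leaves room for the same loss but does not require it.

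**Conclusion.** The point holds as a minor one. Section 10.1 requires removal from the whole study for an event it attributes to one bundle element, and none of sections 5.2, 5.2.1, 7.2, 8.1 or 10.4 continues actigraphy or record-based outcomes afterwards. The direction is a mild tilt towards the Intervention Phase and a risk of understating feasibility failures, with or without replacement.

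The size is small. One or two removals shift the Intervention mean by 0.005 or 0.010 against an anticipated 0.20, assuming all occur before extubation and the removed children would have stayed at 0.50; the shift is about half that if they would have reached 0.60 or if only half are removed before extubation. Removals of 10% or 15% are included only to show the range; nothing in the plan supports them, and the exclusion of at-risk children points to a low frequency. Each uncounted removal is worth 1/40 = 2.5 percentage points of feasibility. The standard-error rise applies only if removed children are not replaced. The study is an unpowered pilot, so what is affected is the feasibility result and the preliminary estimates, not a confirmatory test.

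**What to change.** In 10.1, replace the removal wording with: *bolus feeding, and any other bundle element the clinical team judges unsafe, will be stopped; unless consent is withdrawn or the investigator withdraws the child for safety, the child remains enrolled for actigraphy and record-based outcomes to PICU discharge or Day 28, is analysed in the phase of enrolment, and is counted as unable to continue the feeding element.*

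In 5.2, add: *stopping a bundle element for an adverse event or non-adherence is not in itself withdrawal from the study.* The investigator's existing right to withdraw a child for safety stays.

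The cost is minor amendment wording in two places and continued collection of data already planned. No new measurement is needed, and the clinical team's freedom to stop feeds or other elements is not reduced.
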